2.0 Background

There are considerable and persistent racial disparities in prostate cancer outcomes. Prostate cancer disproportionately affects African American men in terms of incidence, morbidity, and mortality (1), even after adjustment for stage (2), as African American race is perhaps the most consistent risk factor for prostate cancer. Reduced access to health care services also contributes to racial disparities in prostate cancer outcomes, but even in equal access health care systems such as the Veterans Administration (VA), African American Veterans have higher serum PSA values and higher-grade tumors than white Veterans (3,4), even when presenting at the same stage of disease. Thus, access to health care is necessary but not sufficient for eliminating racial differences in prostate cancer outcomes. A better understanding of the biological mechanisms underlying these disparities is needed to develop strategies to overcome them. Vitamin D-mediated biological and biochemical actions are of great interest from the standpoint of racial disparities in prostate cancer outcomes because differences between African American and Caucasian men mirror racial differences in vitamin D levels (5).

Vitamin D and Prostate Cancer: Prostate cells express the vitamin D receptor (VDR), vitamin D-25-hydroxylase, 25-hydroxy-vitamin D-1-alpha-hydroxylase and the 25-hydroxyvitamin D-24-hydroxylase (8-13). Therefore, normal prostate cells can synthesize 25(OH)D (calcidiol) from vitamin D₃ (cholecalciferol), and 1,25(OH)₂D (calcitriol) from 25(OH)D (calcidiol) (14, 15). 1,25(OH)₂D is the hormonal, most potent form of vitamin D and in prostate cells it acts in a paracrine/autocrine fashion.

Several mechanisms of vitamin D-mediated anti-cancer action have been identified (16). Calcitriol induces cell cycle arrest through the expression of insulin growth factor binding protein-3 (IGFBP-3), which increases the levels of the cell-cycle inhibitor p21 in LNCaP prostate cancer cells (17); calcitriol also activates expression of IGFBP-3 by direct transcriptional stimulation through a vitamin D response element (VDRE) located in its promoter sequence (18). VDRE sequences have also been demonstrated in the promoter of the tumor growth factor beta (TGF β)-2 gene (19), and treatment of PC-3 prostate cancer cells with TGF β leads to enhanced expression of IGFBP-3 and subsequent growth arrest and apoptosis (20). Additional studies have suggested a link between chronic inflammation and prostate cancer (21). Vitamin D suppresses the expression of cyclooxygenase-II (COX-2), the key enzyme for the synthesis of prostaglandins, mediators of inflammation and thought to be important for cancer progression (22); COX-2 expression in biopsy cores and prostate cancer surgical specimen is an independent predictor of recurrence (23). Furthermore, there is considerable evidence that calcitriol inhibits nuclear factor kappa-light-chain-enhancer of activated B cells (NF κ B) signaling, and decreases the levels of the angiogenic and pro-inflammatory cytokine interleukin-8 (IL-8) in prostate cancer cells (24). NF κ B is a transcription factor that plays a central role in the control of inflammation and is expressed at high levels in prostate cancers with high Gleason scores (25). This is only a very limited list of the many molecular pathways and mechanisms affected by vitamin D, as it is now well established that VDR may recognize cognate VDRE present within the regulatory sequences of hundreds of human genes, implicating vitamin D in a vast network of gene regulation, and underlying its broad physiological actions (26, 27). The recent emphasis on non-skeletal functions of vitamin D has to do with the realization that vitamin D deficiency has major implications for human health in general, and cancer biology in particular (32).

Hypovitaminosis D in African American Populations: Exposure of skin to sunlight in the ultraviolet B (UVB) range of the spectrum (290 to 315 nm) results in the photolytic conversion of 7-dehydrocholesterol to previtamin D₃, which is transformed to vitamin D₃ (cholecalciferol) by thermally induced isomerization (28, 29). Vitamin D₃ can be obtained from the diet; however, it is distributed very poorly in natural foodstuffs. Dark skin pigmentation, due to melanin, probably evolved in equatorial regions to protect individuals from skin cancers. Increased skin pigmentation, however, limits one's ability to produce vitamin D₃ (30). Vitamin D deficiency occurs when serum levels of 25(OH)D are at <50 nmol (<20 ng/mL); as a result, a majority of

African-Americans are vitamin D-deficient (4). We recently published the results of a prospective clinical study aimed at examining the effects of vitamin D₃ supplementation at 4,000 IU per day for two months in male subjects who had selected surgical removal of the prostate (prostatectomy) as a definitive treatment for their prostate cancer. According to current standard of care, a two-month interval between biopsy and prostatectomy is needed to resolve the inflammation due to the biopsy procedure. Moreover, the initial two months of vitamin D₃ supplementation register the fastest rise in serum levels of 25(OH)D, as reported by us (31,32) . This prostatectomy study was aimed at investigating the effects of vitamin D₃ supplementation (4000 IU per day for two months) on prostate tissue specimens obtained at surgery, by means of RNA-seq technologies, with special emphasis on differential gene expression in African American men compared to Caucasian men, and between supplemented and placebo groups (33). This paper is available in PDF format as Appendix 1.

We set Caucasian subjects (17 samples) as the control and African American subjects (10 samples) as the test. The results of our analyses showed that 3107 genes were differentially expressed using a stringent (highly significant) FDR<0.1, and 8237 genes were differentially expressed using a less stringent (still significant) FDR<0.4. Pathway analysis using the 3107 differentially expressed genes highlight major differences between the two groups, with African American showing higher expression of genes associated with immune response and inflammation. It must be noted that our observations are consistent with a previous report (34) based on the analysis of prostate tissue-derived RNA, performed using Affymetrix microarrays. This analysis revealed enhanced expression - in tissue samples from African American subjects - of biological pathways that are linked to autoimmune diseases, allergies, and inflammatory diseases. Even at this preliminary stage the results of our RNA-seq studies support the existence of considerable biological differences within the prostate between African American and Caucasian men and suggest that overexpression of genes linked to the inflammatory process may very well contribute to the increased severity and faster progression of prostate cancer in African American men, even at the early stage of disease (33).

Stress Response and Allostatic Load:

Allostatic load defines a set of clinical and biochemical parameters that can be easily measured in a basic clinical setting (35). These parameters can be analyzed to gauge the level of stress experienced by each subject. These values reflect chronic, steady state levels of stress as well as failure to shut-off responses to acute stressors. To the best of our knowledge, there is only one published report of a correlation between allostatic load in African American subjects and specific biomarkers (36). This report identified the dopamine receptor gene, *DRD4*, and the serotonin transporter gene, *SLC6A4*, as indicators of stress, because of a non-supportive family environment. Interestingly, both of these genes were very significantly up-regulated (at a FDR<0.1) in prostate tissue samples from African American men. These considerations suggest that the prostate appears to be, even at the molecular level, a "sentinel" organ for chronic stress.

The results of our RNA-seq analyses are consistent with our study objectives. These preliminary indications make us confident that the acquisition of additional RNA-seq data will allow us to strengthen the significance of our findings and help us identify specific pathways for possible targeted intervention.

Genomic technologies can be easily applied to the prostate tissue samples obtained from eligible subjects, undergoing prostate biopsy as part of their standard medical care. The results of our preliminary studies have already shown significant differences in the transcription profiles in prostate tissue samples between African American and Caucasian men. In addition, special emphasis will be given to RNA-seq analyses of Hypothalamic-Pituitary-Adrenal (HPA) -related transcription profiles, measurements of allostatic load and comparison of these profiles by race.

4.0 Study Endpoints

We will be investigating Veterans who are undergoing prostate biopsy. If the Veterans are eligible and seek active surveillance as their treatment modality, they will be offered an opportunity to receive 4,000 IU Vitamin D supplementation as per previous protocol. Upon repeat biopsy (standard of care), they will have repeat RNA-seq analyses which will serve as further internal control. We will be measuring serum prostate specific antigen (PSA) as per standard of care recommendations. A blood sample for ancestry markers will be collected at the conclusion of the study.

Primary clinical endpoint: We will be assessing for clinical activity based on PSA changes, and investigating whether or not vitamin D supplementation results in a 20% decrease from baseline PSA.

5.0 Inclusion and Exclusion Criteria/ Study Population

Males only, due to the limitation of the study to prostate tissue

Part 1

Inclusion Criteria

- a) Age: 50 - 75 years of age
- b) Scheduled to undergo a standard of care prostate biopsy because of an elevated PSA, an abnormal DRE (digital rectal exam) or other diagnostic procedure.
- c) Permission for investigators to follow subject's post biopsy diagnosis, treatment decision and follow/up care (including subsequent prostate biopsies).

Exclusion criteria:

Inability or unwillingness of subject to give informed consent

Part 2

Inclusion Criteria

- a) Prostate biopsy pathology report with diagnosis of prostate cancer
- b) Treatment recommendation and/or subject decision of active surveillance
- c) Agreement to take vitamin D₃ 4000 IU daily for approximately one year
- d) Standard of care repeat PSA at six months and surveillance (repeat) prostate biopsy after one year

Exclusion Criteria

- a) Initial testing of prostate biopsy core sample indicates non-viable RNA for further sequencing.
- b) Current vitamin D supplementation > 2000 IU daily
- c) Inability or unwillingness to continue as a participant in the study

6.0 Number of Subjects

In an ongoing RNA-seq study of prostate tissue, 28 % of the enrolled subjects had pathology results of prostate cancer with the potential of active surveillance as the treatment option. Therefore, for this study, 250 African American and Caucasian males will enroll in Part 1 of the study with the goal of 60 African American and Caucasian males participating in Part 2. There may be less than 250 subjects in Part 1 if Part 2 accrues more quickly.

7.0 Setting

- Subject recruitment/enrollment will be conducted at the Ralph H. Johnson VA Medical Center's Urology Clinic and Research Offices/Clinics.
- The allostatic load blood analysis will be conducted by the Ralph H. Johnson Laboratory Services and MUSC's Laboratory Services
- The Vitamin D serum analysis will be conducted by [name] Laboratory at MUSC.

- RNA purification from biopsy tissue specimens will be performed at the Hollings Cancer Center Biorepository and Tissue Analysis Shared Resource. The RNA-seq will be performed by [name] Genomics Core Laboratory, Queens University Belfast, Ireland.

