Male subjects (up to 250 in Part 1) will be enrolled in this study when they have their scheduled prostate biopsy. Pathology results at enrollment will be unknown. However, they will be followed to obtain data as to the biopsy results, treatment options, if recommended, for definitive treatment and/or management. For this project, in Part 2, sixty eligible subjects will be enrolled. Therefore, a total of 60 prostate tissue samples will be analyzed at baseline and again at study exit (repeat prostate biopsy). We anticipate that approximately 20 African American subjects will be enrolled in the study, since approximately 40% of the patients seen in the Urology Clinics of the Ralph H. Johnson VA Medical Center in Charleston are African American. As shown under Preliminary Studies, major differences in transcription within the prostate were observed between African American and Caucasian subjects enrolled in the pilot study (33).

Tissue Sample Procurement: The PI will oversee the procurement of prostate tissue core specimens. Specifically, he will orchestrate the single added core sample from a peripheral area of the prostate, during the enrolled subjects' prostate biopsy. This will ensure that the excision of tissue samples does not interfere with the diagnostic priorities.

RNA Purification, Sequencing, and Analysis of Transcription Profiles: This project will rely on several facilities. The Hollings Cancer Center Biorepository and Tissue Analysis Shared Resource will purify total RNA from each de-identified tissue sample using standard procedures. RNA integrity will be verified using RNA 6000 Nano Assay chips run in Agilent 2100 Bioanalyzer

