(Agilent Technologies, Palo Alto, CA). High-quality RNA will be divided into two de-identified-coded samples and forwarded for storage to the Principal Investigator's Laboratory at the Charleston VAMC. Only one of the two split samples will be bulk shipped to [name] Genomics Core Laboratory at City of Hope Comprehensive Cancer Center in Duarte, CA. for RNA-sequencing. 100-200 ng of total RNA will be used to prepare RNA-Seq libraries using the TruSeq RNA Sample Prep Kit (Illumina, San Diego, CA) following the protocol described by the manufacturer. Paired end cluster generation will be performed on the cBot as described by the manufacturer (Illumina, San Diego, CA). Clustered RNA-seq libraries will be paired end sequenced with 250 cycles on a HiSeq2500 (Illumina, San Diego, CA). This new instrument acquired recently by MUSC generates up to 1 Tb per run, with data yields typically containing 80% greater than Q30, 2 x 100 bp read length. The "paired end" approach will be employed for the RNA-seq experiments, wherein a single long read is sequenced for 100 nucleotides at both ends. In addition to providing digital mRNA profiling, this strategy will permit tracking alternate splice junctions, insertions and deletions, and facilitate transcriptome assembly in these prostate cells and experimental groups.

Each sample will be sequenced to a depth of 100 million reads. Adapters will be trimmed by Trimmomatic (38). Alignment and annotation will be performed using DEseq2 (39), Edge R (40, 41) and the Tuxedo Suite comprising Bowtie2, Tophat2 and Cufflinks2 (42). As we are interested in applying RNA-seq as a discovery tool, the Tuxedo Suite will facilitate the identification of alternative splicing events, allele-specific expression, and rare and novel transcripts in these mRNA data sets.

Sample Size Estimation: The sample size of this study is 250 (Part 1) and 60 (Part 2) based on practical considerations and reasonable statistical power. Our inferences will be based on the determination of threshold on *p*-values to achieve a false discovery rate (FDR) of 10%. We anticipate that the large majority of genes will not be significant, but do not know the *p*-value threshold; we expect it to be between 0.001 and 0.01.

The primary endpoint is to estimate PSA reduction between pre and post treatment. We expect 20% PSA reduction post-treatment with the standard deviation of 40%. With 60 subjects, the 95% confidence interval for the estimated PSA reduction is 10% to 30%.

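### The protocol gives conflicting sites for RNA sequencing and has no rule keeping a man's baseline and exit samples in one batch, so a batch shift could be partly or wholly confounded with the before/after vitamin D contrast.

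*Combined protocol and SAP*

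**What the plan says.** Three statements about the sequencing site stand in the current text:

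- Section 7.0 (Setting) says that the sequencing will be done by the "Genomics Core Laboratory, Queens University Belfast, Ireland".
- Section 10.0 (RNA Purification, Sequencing, and Analysis of Transcription Profiles) sends the RNA to the "Genomics Core Laboratory at City of Hope Comprehensive Cancer Center in Duarte, CA. for RNA-sequencing".
- The same paragraph of Section 10.0 then describes the sequencer: "This new instrument acquired recently by MUSC generates up to 1 Tb per run".

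On handling, Section 7.0 states: "RNA purification from biopsy tissue specimens will be performed at the Hollings Cancer Center Biorepository and Tissue Analysis Shared Resource". Section 10.0 agrees on that site and adds: "High-quality RNA will be divided into two de-identified-coded samples and forwarded for storage", at the Charleston VAMC. It continues: "Only one of the two split samples will be bulk shipped to" the sequencing laboratory.

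On the paired design, Section 10.0 (Patient Cohort) states: "a total of 60 prostate tissue samples will be analyzed at baseline and again at study exit". Section 4.0 presents the repeat sequencing as an added internal control. The two cores are about a year apart (Section 5.0, Part 2, and the flowchart).

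On analysis, Section 10.0 (Data Analytic Approaches) plans a DESeq2 negative binomial model with Wald tests of group contrasts at a false discovery rate of 10%, with edgeR as confirmation. No design formula is written out. Neither subject, laboratory nor batch is listed as a term.

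**The concern.** Sequencing laboratory, library preparation and run can each shift measured expression gene by gene. In a paired design the shift cancels if both samples of a man go through the same batch. If they do not, it enters the difference between exit and baseline.

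That difference is also the within-man vitamin D contrast, and Part 2 has no concurrent unsupplemented arm against which to recognise a shift. The text gives two reasons to ask. The sites conflict, which raises the possibility that the laboratory changed during the study. Section 10.0 also describes sample analysis as continuing work with evolving methods, so sequencing baseline samples before the exit cores exist is not excluded. Bulk shipment does not say whether there is one shipment or several, or whether pairs travel together.

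What is at stake is the before/after part of Objective 2. The race comparison in Objective 1 would be biased only if the race mix differed across batches.

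**Working it through.** **The plan's own figure.** The only design calculation concerns PSA: mean reduction 20%, SD 40%, n = 60. Then 20 ± 1.96 × 40/√60 = 20 ± 10.1, or 9.9% to 30.1%. The stated 10% to 30% reproduces and is not in dispute. There is no corresponding figure for RNA-seq.

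**Side by side.** Sections 7.0 and 10.0 each name one sequencing laboratory, and the names differ. The institution names are intact, so removed text does not explain the conflict. The MUSC sentence adds a third institution. No sentence allocates some samples to one site and some to another. The purification site is consistent throughout.

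**Illustration: fixed shift, every pair split.** From Section 10.0: n = 60 pairs and an expected p-value threshold between 0.001 and 0.01. Assumed, because the documents give no value: the size of the shift, in SDs of the paired difference, for a gene that vitamin D does not affect. The calculation is a normal approximation, not the planned Wald test.

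- Shift giving a 50% chance of a call = z/√60. At p = 0.01: 2.576/7.746 = 0.33 SD. At p = 0.001: 3.291/7.746 = 0.42 SD.
- Chance of a call at a 0.5 SD shift = P(Z > z − 0.5 × 7.746) = P(Z > z − 3.873). At p = 0.01: P(Z > −1.297) = 0.90. At p = 0.001: P(Z > −0.582) = 0.72.

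**Same shift, half of the pairs split.** The mean shift falls to 0.25 SD, and 0.25 × 7.746 = 1.936. At p = 0.01: P(Z > 0.640) = 0.26. At p = 0.001: P(Z > 1.355) = 0.09. This ignores the slight extra variance from mixing split and unsplit pairs, which would lower both figures a little.

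**Illustration across genes.** All of these inputs are assumptions: 15,000 genes, no true effect, SD of the paired log2 difference s = 0.7 or 1.0, and gene-specific shifts drawn from a normal distribution with mean 0 and SD τ. Paired t-tests were run with Benjamini-Hochberg at 10%, averaged over five simulation runs. False discoveries, s = 0.7 / s = 1.0:

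| τ | all pairs split | half split |
|---|---|---|
| 0 (pairs kept together) | 0 / 0 | 0 / 0 |
| 0.1 | about 910 / 80 | about 4 / 0.4 |
| 0.2 | about 5,800 / 2,900 | about 730 / 46 |
| 0.3 | about 8,650 / 6,200 | about 3,200 / 960 |

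An analytic check at τ = 0.2 with all pairs split: the mean difference has variance τ² + s²/60, so its SD exceeds the nominal s/√60 by a factor r = √(1 + 60τ²/s²). For s = 0.7, r = 2.43, and the share of null genes flagged is 2 × P(Z > z/r), which is 18% at p = 0.001 and 29% at p = 0.01. For s = 1.0, r = 1.84, giving 7% and 16%. The nominal rates are 0.1% and 1%.

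**When modelling can help.** If every baseline sample is in one batch and every exit sample in another, batch and time are the same column of the design matrix and cannot be separated. If only some pairs are split, the unsplit pairs identify the time effect, and a batch term can be estimated at a cost in precision.

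**The case against.** The best defence is that the text describes no splitting. Each section names a single laboratory, and the conflict, including the MUSC sentence, may be wording left over from an earlier arrangement. The workflow of one purification facility, storage at the VAMC and then bulk shipment fits accumulating samples and sequencing them together. The retained aliquot could allow bridging or a re-run. Enrolment is rolling, with up to 250 men entered to reach 60, so early exit samples might travel with later baseline samples and confounding would be partial. The missing batch term reflects a model that is not fully written out, rather than a stated decision to omit it. RNA-seq here is for discovery, and the primary endpoint is PSA.

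Most of this stands and limits the point. It does not remove it. The two site statements cannot both be followed, and storage makes co-batching feasible without requiring it.

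A reader might go further and infer that baseline samples go to one laboratory and exit samples to another, so that the before/after comparison fails altogether. The documents do not support that, because no sentence orders it. A reader might also take this comparison to be the only molecular evidence on supplementation. Objective 2 in Section 1.0 also plans comparisons by serum level and by supplementation status, so it is the within-man evidence that is exposed. Nor does anything in the documents link race to calendar time or shipment. Bias in the race comparison is a possibility to guard against, not a finding.

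**Conclusion.** The contradiction over the sequencing site is explicit and has to be resolved. The absence of a pairing rule, and of subject and batch terms, is an omission that leaves the before/after RNA-seq contrast open to confounding that could be partial or complete. Whether it would happen cannot be told from the documents.

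The size is conditional. With 60 pairs all split, a 0.5 SD shift would lead to an unaffected gene being called 90% of the time at p = 0.01 and 72% at p = 0.001. With half split, the figures are roughly 26% and 9%. With pairs kept together, the shift cancels. These figures rest on assumed shifts and a normal approximation, and they show sensitivity rather than likelihood. The PSA endpoint and its interval are unaffected. The change should be made because it is cheap and because the worst case cannot be repaired by modelling.

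**What to change.** - Name one sequencing laboratory and one platform, identically in Sections 7.0 and 10.0, and correct or remove the MUSC instrument sentence.
- State that the stored baseline RNA of each Part 2 man is held, and that his baseline and exit samples are prepared and sequenced in the same batch, with race balanced across batches.
- Write out the model. The before/after DESeq2 and edgeR analyses need a subject term, which absorbs batch when pairs are kept together. The between-race model needs a batch term, as does any before/after analysis that includes a split pair.
- If two laboratories have already been used, report which samples went where, and use the retained aliquots for bridging or re-sequencing.

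The cost is protocol wording and shipment planning. The main downside is that baseline sequencing results for Part 2 men wait about a year, until the exit core is available. Eligibility need not wait, since the RNA viability criterion in Section 5.0 rests on initial testing of the core rather than on sequencing. Held baseline RNA will have been stored longer than exit RNA, so RNA integrity should be rechecked and recorded for both when libraries are prepared.
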